9.6.1 Treatment-Emergent Adverse Events

AEs will be coded using the *Medical Dictionary for Regulatory Activities* (MedDRA). The system organ class and preferred term for each AE will be available, along with the verbatim reported term, event start and stop dates/times, seriousness, severity, relationship to treatment/device, action taken, and event outcome. SAEs will also be documented in a case narrative format.

The overall numbers and percentages of subjects who experienced any treatment-emergent AEs (TEAEs) will be presented. TEAEs will also be summarized at the subject level by system organ class and preferred term, and at the event level by system organ class/preferred term and severity and by system organ class/ preferred term and relationship to treatment.

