3.4 Study Rationale

This clinical study will evaluate the use of MB-102 and the MediBeacon[®] Transdermal GFR Measurement System for the purpose of marketing application with the final device design.

4 Study Objectives

The objectives of this pivotal study are:

- To establish that the MB-102 transdermal fluorescence measured GFR using the MediBeacon[®] Transdermal GFR Measurement System is comparable to the measured MB-102 plasma GFR
- To evaluate the safety and tolerability of a single dose of MB-102 in subjects
- To evaluate the safety and effectiveness of the MediBeacon[®] Transdermal GFR Measurement System for the non-invasive transdermal fluorescence detection of MB-102 in subjects

5 Investigational Plan

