- Moderate: Results in moderate transient impairment of a body function or transient damage to a body structure and/or requires intervention, such as administration of medication or transfusion or laparoscopic or endoscopic procedure to prevent permanent impairment of a body function or damage to a body structure.

Severe: An event which is life threatening, results in permanent impairment of a body function or permanent damage to a body structure or necessitates significant intervention, such as major surgery, to prevent permanent impairment of a body function or permanent damage to a body structure. The term severe is often used to describe the intensity (severity) of a specific event (as in mild, moderate, or severe myocardial infarction); the event itself, however, may be of relatively minor medical significance (such as severe headache). This is not the same as serious, which is based on patient/event outcome or action criteria usually associated with events that pose a threat to a patient's life or functioning. Seriousness (not severity) serves as a guide for defining regulatory reporting obligations. An event that changes in severity (gets worse or gets better) should be noted as its worst severity.

Assessment of Causality

Every effort will be made by the investigator to assess the relationship of the AE, if any, to the study device (and components), investigational drug. Causality should be assessed using the categories presented below:

| Unrelated | Clinical event with an incompatible time relationship to study device or study drug, and that could be explained by underlying disease or other drugs or is incontrovertibly not related to the study device. |
|-----------|---|
| Unlikely | Clinical event whose time relationship to study device investigational drug makes a causal connection improbable, but that could plausibly be explained by underlying disease or other drugs. |
| Possible | Clinical event with a reasonable time relationship to study device or investigational drug, but that could also be explained by concurrent disease or other drugs. |
| Probable | Clinical event with a reasonable time relationship to study device or investigational drug and is unlikely to be attributed to concurrent disease or other drugs. |

Very Likely/Certain Clinical event with plausible time relationship to study device or investigational drug, and that cannot be explained by concurrent disease or other drugs.

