8.1 Investigational Drug

Clinical data from the Pilot 1A and 1B studies (total n = 32 subjects) included the following adverse events:

- Pilot 1A (n = 16)
 - Vasovagal reaction (1 subject)
 - Dizziness (1 subject, 2 events)

These events occurred in fasting subjects shortly after dosing and resolved on that day. No other AEs, injection site reactions, clinically significant laboratory values or significant changes in vital signs were noted during this study.

- Pilot 1B (n = 16)
 - Headaches (56.3% of subjects)
 - Erythema (at the site of the adhesive) (100% of subjects)
 - Diarrhoea (1 subject)
 - Dizziness (occurring in 1 subject following release from the study center)

Erythema was thought to be related to the adhesive used to adhere the sensor to the skin. Headaches were deemed related to the head strap required to hold the forehead sensor in place. Sensor placement on forehead was discontinued post Pilot 1B.

MB-102 is excreted in the urine. Therefore, urine discoloration (chromaturia) is expected but has not been considered an adverse event in prior studies.

In the Pilot 2 study, a total of 234 subjects with normal to compromised renal function have been exposed to MB-102. A total of 120 subjects received a dose of 4 μ mol/kg followed by a 5 mL injection of iohexol. Seventy (70) subjects received a single dose only (no iohexol) of 4 μ mol/kg of MB-102) and 44 have received a fixed dose of 130 mg (7 mL). All reported AEs were mild or moderate in severity and resolved without sequalae. Overall, MB-102 given in conjunction with or without iohexol was well tolerated in this subject population.

A total of 40 adverse events were reported in 28 treated subjects in Groups 1, 2 and 3 for an AE rate of 12.0% in the treated population. A total of 31 events were considered mild and 9 moderate events occurred in 5 subjects (2.5% of the population). There were no severe events

reported. There were no Serious Adverse Events (SAEs) reported during the study. There were no Unanticipated Adverse Device Effects (UADEs) reported during the study.

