Four AEs, dyspepsia, chromaturia, hot flush and (facial) rash were considered related to investigational product (MB-102); all events resolved by study completion. Dyspepsia and chromaturia were also considered to be related to iohexol. Of note, chromaturia is an expected effect of MB-102 (noted in the Investigator's Brochure) and expected in all subjects as the excretion of MB-102 will color the urine of subjects receiving the product. It is not a documented effect of iohexol (per the label).

Seven (7) AEs occurring in 7 subjects were considered related to the device (sensor attachment); these included application site erythema, dermatitis, and pruritus and were considered related to the adhesive material used to hold the sensor in place. Two events of application site discoloration (melanin spot at the sensor location) were noted in 2 subjects in the SOG cohort which resolved within 24 hours of removal of the sensor. Other reported AEs (conjunctivitis, nausea, vomiting, cardiac murmur, headache, anxiety, micturition urgency, pollakiuria, urine odor abnormal, peripheral oedema, fatigue, and a pruritis event [not at the sensor location] were considered not related to MB-102, the sensor device or iohexol. Injection site reactions (bruising, erythema, extravasation) were also not considered related to MB-102.

There may also be other risks that are unforeseen at this time. For additional information on the risk profile, please reference the current Investigator's Brochure.

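### Section 9.6.1 tabulates TEAE severity and relationship by event only, so no count of subjects with a related or a moderate-or-worse TEAE is planned

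*Combined protocol and SAP*

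**What the plan says.** Section 9.6.1 plans two summaries by subject. The first is overall: "The overall numbers and percentages of subjects who experienced any treatment-emergent AEs (TEAEs) will be presented". The second is by term: "TEAEs will also be summarized at the subject level by system organ class and preferred term". Neither is split by severity or cause. The same sentence then places severity and relationship "at the event level by system organ class/preferred term and severity and by system organ class/ preferred term and relationship to treatment".

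Earlier in section 9.6.1, the data listed for each AE include severity and relationship to both treatment and device. The planned relationship table names treatment only.

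Section 7.1.2.1 has a worst-severity rule: "An event that changes in severity (gets worse or gets better) should be noted as its worst severity". It also sets five causality categories, from unrelated to very likely/certain, and asks for related AEs to be assessed further for attribution to drug or device where possible.

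Section 4 gives the drug safety objective: "To evaluate the safety and tolerability of a single dose of MB-102 in subjects". A further objective covers the safety and effectiveness of the device. Section 9.6 evaluates the safety of both through TEAEs, with emergence counted from the first dose for the drug and from sensor placement for the device.

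**The concern.** Two of the three objectives concern safety, and the trial has one arm. With no comparator, grade and attribution carry much of the interpretation. An any-cause, any-grade percentage mixes drug and device effects with procedural events: section 8.3 expects bruising at the catheter site, and sections 6.6 and 8.3.1 require every extravasation to be recorded as an AE.

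The natural summaries are the shares of dosed subjects with at least one TEAE related to MB-102, with at least one related to the device, and with at least one of moderate or worse severity. An event count has no subject denominator and can include one person several times. Re-enrolment under section 6.11 adds a route to this: a subject may enter twice under one ID, and a subject re-enrolled after an extravasation already has an AE on record.

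At stake is the description of safety in the report. The P30 endpoint and its success criterion are not affected.

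**Working it through.** **Step 1. Planned outputs side by side (section 9.6.1).**

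| Summary | Unit | By severity | By relationship |
|---|---|---|---|
| Any TEAE | Subject, n (%) | No | No |
| SOC and PT | Subject | No | No |
| SOC/PT and severity | Event | Yes | No |
| SOC/PT and relationship to treatment | Event | No | Yes |

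No row gives subjects by severity or by relationship. The worst-severity rule in section 7.1.2.1 does not fill the gap, because it grades one event that changes over time and does not pick the worst grade across a subject's events. Section 9.6.3 refers to a Statistical Analysis Plan for details of the laboratory summaries; section 9.6.1 makes no such reference. No other section plans these counts.

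**Step 2. Reproduce the protocol's own figure (section 8.1, Pilot 2).** Inputs: 234 subjects exposed; "A total of 40 adverse events were reported in 28 treated subjects in Groups 1, 2 and 3 for an AE rate of 12.0"%. Subject-level rate = 28/234 = 11.97%, which rounds to the stated 12.0%.

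**Step 3. Events against subjects in Pilot 2.**
- Moderate: "A total of 31 events were considered mild and 9 moderate events occurred in 5 subjects". Events per affected subject = 9/5 = 1.8. Events per 100 treated = 100 × 9/234 = 3.8. Subjects = 5/234 = 2.1% (exact 95% CI 0.7% to 4.9%).
- Device-related: "Seven (7) AEs occurring in 7 subjects were considered related to the device (sensor attachment". Events per affected subject = 7/7 = 1.0, and 7/234 = 3.0% on either count.

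Section 8.1 puts the 5 subjects at 2.5% of the population. On 234 they are 2.1%; 2.5% would need a denominator of 200. That is a separate matter, and only the counts are used here.

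**Step 4. Keep denominators apart.** The moderate share of all events is 9/40 = 22.5%. Its ratio to 2.1% of subjects is (9/40)/(5/234) = (9/5) × (234/40) = 1.8 × 5.85 = 10.5. Repeat counting supplies the 1.8; the 5.85 is only the change from events to treated subjects. Like for like, the comparison is 3.8 per 100 against 2.1%, or 22.5% of events against 5/28 = 17.9% of subjects with an AE.

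**Step 5. What an event total leaves open.** Assume, for illustration, 9 moderate events in this trial. Taken alone, that total fits anything from 1 to 9 subjects:
- on 188 subjects (the evaluable target): 1/188 = 0.5% to 9/188 = 4.8%;
- on 250 subjects (the enrolment cap): 1/250 = 0.4% to 9/250 = 3.6%.

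**The case against.** Several points on the other side stand.

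- **The trial could still report these shares.** A reader might infer that it will not or cannot. The documents do not support that: severity and relationship are held for every AE, so the shares can be derived later, and the plan mentioned in section 9.6.3 might add the tables. What can be said is that the documents supplied do not plan them.
- **Tolerability as a whole is not distorted.** A reader might infer that repeat events bias the overall safety result. The any-TEAE percentage and the SOC/PT summary count subjects, so repeats cannot inflate them.
- **There is no tenfold inflation.** Setting 22.5% beside 2.1% mixes denominators (step 4), and section 9.6.1 does not say that the event table will show percentages of all events.
- **Repetition within a term is not shown.** Section 8.1 does not say that the 9 moderate events repeated the same PT in a subject. If the terms differed, PT rows would be the same on either count, and only SOC and overall rows would change. This is why overall rows are needed.
- **The device evidence shows no repeat counting**, and application-site terms would appear in the planned subject-level PT summary. That summary is not filtered by causality, however, so it does not give device-related incidence.
- **Safety carries no hypothesis or success criterion.** This limits the weight of the point. It does not remove the need for incidences that serve the stated objectives.

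**Conclusion.** The point holds in a limited form. Section 9.6.1 makes an explicit choice to tabulate severity and relationship by event, and its relationship table does not name the device. Followed as written, the documents supplied plan no incidence of MB-102-related, device-related, or moderate-or-worse TEAEs among subjects.

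The effect is confined to the severity and relationship tables, and its size cannot be known in advance. Pilot 2 shows both outcomes: a factor of 1.8 for moderate events (3.8 per 100 treated against 2.1% of subjects) and none for device-related events (7 in 7). The conclusion rests on reading the event-level wording literally and on the text supplied, without any separate SAP. It should be changed, but it does not threaten the primary analysis.

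**What to change.** In section 9.6.1, add Safety Population tables of n (%) of subjects, overall and by SOC/PT:

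- (a) by worst severity per subject;
- (b) with at least one TEAE related to MB-102 and, separately, with at least one related to the device, each using its own definition of treatment emergence from section 9.6.

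State the counting rules in advance:

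- Each subject ID counts once, including subjects re-enrolled under section 6.11. Section 9.6 speaks of subjects receiving a single dose, while section 9.2 takes in everyone enrolled and dosed, so the handling of anyone dosed twice should be explicit.
- Name which of the five causality categories in section 7.1.2.1 count as related.
- Give related events that cannot be attributed to drug or device their own row.

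Keep the event-level tables as support. The cost is a wording change and two or three extra tables from data already collected, with no new data, visits or subjects.

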9.6.2 Physical Examinations/Limited Physical Assessments

The results of physical examinations will be collected as adverse events if clinically significant or as medical history (if observations are noted prior to TGFR start). Physical exam data will not be listed.

9.6.3 Clinical Laboratory Assessments

Clinical laboratory tests include clinical chemistry, hematology, urinalysis and coagulation parameters. Each parameter will be summarized using the descriptive statistics. Details will be specified in the Statistical Analysis Plan (SAP). Also, individual subject results will be assessed against an appropriate reference range if available. The manifestation of any clinically significant abnormality that develops during the study will be reported as an AE.

9.6.4 ECGs

ECG data will be listed. Clinically significant findings will be noted as adverse events.

9.6.5 **Prior and Concomitant Therapies**

Concomitant medications administered within 3 days prior to MB-102 dose administration and through the follow-up study visit will be listed. Medications will be coded using the World Health Organization (WHO) drug dictionary. Data will be provided in one or more subject data listings. Concomitant non-drug therapies will be listed.

9.7 Determination of Sample Size

For a P30 true value of 0.95, alpha of 0.025, performance goal of 85%, power of 90%, the one-sided exact binomial test yields a sample size of 102.

9.8 Missing Data

Missing values will not be imputed.

9.9 Analysis Phases

The global study will include 188 evaluable subjects. The US enrolment will have 140 evaluable subjects. Once the US sites have enrolled the targeted number of evaluable subjects, the US clinical sites will be closed. The US data alone may be used to support the market authorization and approval in the US. The completed OUS dataset, if available will be included in the US application.

10 Quality Assurance and Quality Control

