| Number of Treated Subjects: | Up to 250 subjects are planned for enrollment. The US sites will plan to enroll at least 140 evaluable subjects; Chinese sites will plan to enroll at least 48 evaluable subjects. The population will be split into stratums in accordance with screening eGFR measured by the CKD-EPI equation: | | | | |
| | • Stratum 1: 50% of evaluable subjects with an eGFR \ge 70 mL/min/1.73 m ² | | | | |
| | • Stratum 2: 50% of evaluable subjects with an eGFR < 70 mL/min/1.73 m^2 | | | | |
| | Approximately 50% of subjects within each Stratum enrolled in the US will be Fitzpatrick skin scale (FSS) I-III and 50% of subjects will have FSS IV-VI. Subjects in the US will be enrolled across a spectrum of both eGFR ($<120 - >15$ mL/min/1.73 m ²) and FSS. | | | | |
| | Subjects enrolled in China will also be represented across the same spectrum of eGFR (<120 - >15 mL/min/1.73 m ²) however the FSS will not apply. This is because the Chinese subject demographic is unlikely to represent the full FSS spectrum. Subjects with incomplete assessments or major protocol deviations may be replaced. Thus, a maximum of 250 subjects may be enrolled. | | | | |
| Treatment: | Eligible subjects in stratums 1 and 2 will receive a single 130 mg dose of MB-102. | | | | |
| | Blood draws will be taken at pre-defined timepoints and the MediBeacon [®] Transdermal GFR Measurement System fluorescent measurements will be collected over a 12 hour - 24 hour period. | | | | |

| Main Criteria for Inclusion: |
|--|

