5.1 Overall Study Design and Plan

Protocol 100-003 is a multi-center, open-label, pivotal trial studying the safety and pharmacokinetics of MB-102 and the use of the MediBeacon[®] Transdermal GFR Measurement System in normal and compromised renal function subjects with different skin color types comparing tGFR to plasma derived indexed GFR (nGFR).

Approximately 250 subjects are planned for enrollment. The US sites will plan to enroll 140 evaluable subjects; China sites will enroll 48 evaluable subjects. The population will be split into stratums in accordance with eGFR by the CKD-EPI equation.

Subjects will be screened and if deemed eligible, will be enrolled. On treatment day, subjects will have a transdermal sensor placed on their chest, and the MediBeacon[®] Transdermal GFR Measurement System will be initiated to collect background fluorescence. When this is completed, subjects will then receive a single dose of MB-102. Serial PK draws will be collected over a 12 to 24 hour period. Fluorescent measurements will also be collected during this period. For subjects with significant renal compromise, fluorescent measurements will continue until the sensor no longer detects MB-102 in the body. Following completion of the treatment period, subjects will return to the study center approximately 1 week later for a safety follow-up visit.

Subjects who do not complete the study or who have major protocol deviations may be replaced. Up to 250 subjects may be enrolled.

The global study will include 188 evaluable subjects. The US enrolment will have 140 evaluable subjects. Once the US sites have enrolled the targeted number of evaluable subjects, the US clinical sites will be closed. The US data alone may be used to support the market authorization and approval in the US. The completed OUS dataset, if available will be included in the US application.

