9.2 Analysis Populations

The following analysis populations will be defined for the study:

- Intent-to-Measure (ITM) Population The ITM population will consist of all subjects who are enrolled in the study in Stratum 1 & 2 and for whom an end of session tGFR has been calculated, and who have not had any major protocol deviations.
- Modified Intent-to-Measure (mITM) Population The mITM population will consist of all subjects in the ITM population with no outlier PK parameters.
- Safety Population The safety population will consist of all subjects who are enrolled in the study and have been dosed with MB-102.
- Pharmacokinetic (PK) Population The pharmacokinetic population will consist of all subjects who are enrolled in the study and have any PK data.

The mITM population will be the primary analysis set for all effectiveness analyses. The Safety Population will be used for the analysis of all safety variables and baseline characteristics. The PK Population will be used for the analyses of PK data.

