9.5 Primary Endpoint Analysis

The primary endpoint is the performance measure of P30 for transdermal-derived GFR with respect to the plasma-derived indexed GFR, with a 95% confidence interval. The performance goal is 85%. Success for the study will be that the lower limit of the 95% CI is greater than 85%.

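### Does Section 9.9 leave open whether the US-only or the pooled data decide the US claim?

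*Combined protocol and SAP*

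**What the plan says.** Section 9.2 fixes the main effectiveness set: "The mITM population will be the primary analysis set for all effectiveness analyses". That set is the ITM population less subjects with outlying PK parameters, and "The ITM population will consist of all subjects who are enrolled in the study in Stratum 1 & 2", subject to a calculated tGFR and no major deviation. Neither definition is limited by region.

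Section 9.5 gives one criterion: "Success for the study will be that the lower limit of the 95% CI is greater than 85" percent. Section 5.1 states the total, "The global study will include 188 evaluable subjects", and the Synopsis gives the split: "The US sites will plan to enroll at least 140 evaluable subjects; Chinese sites will plan to enroll at least 48 evaluable subjects".

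Section 9.9, which repeats a paragraph of Section 5.1, makes three statements about the US data:
- On when recruitment there stops, it says "Once the US sites have enrolled the targeted number of evaluable subjects, the US clinical sites will be closed".
- On a submission without China, it then allows that "The US data alone may be used to support the market authorization and approval in the US".
- On what happens to the Chinese results, it ends with "The completed OUS dataset, if available will be included in the US application".

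Section 9.7 sizes a single exact binomial test at 102 subjects and ties that number to neither 140 nor 188.

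**The concern.** Two nested datasets could each be put forward for US approval: 140 US subjects, or those 140 plus 48 from China. US recruitment stops at its own target, so US data may be complete first. The trial is open-label, and the monitor shows the tGFR at the site.

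If nobody has fixed which set decides, a sponsor could look at the US result and then choose. A US result just short of the mark could be rescued by adding China, and one just over the mark could be kept apart from a weaker pooled result. At stake are the one-sided 2.5% error rate and a clear answer when the two sets disagree.

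**Working it through.** **Inputs.** Goal 0.85, design P30 0.95, one-sided alpha 0.025, power 90%, exact binomial test (Section 9.7). Sizes are 140 US and 48 China, 188 in all (Sections 5.1, 5.4.1 and 9.9). Two assumptions are added: the interval in Section 9.5 is the exact (Clopper-Pearson) one matching Section 9.7, and P30 is the same in both regions.

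**1. The plan's own figure.** For each n, take the smallest r with P(X ≥ r | n, 0.85) ≤ 0.025; power is P(X ≥ r | n, 0.95). At n = 102, r = 94, the error is 0.0231 and the power 0.930. Power stays at or above 90% from n = 102 onwards, so 102 reproduces.

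**2. Each set alone.**

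| Set | Pass mark | Lower limit at mark / one fewer | Error at 0.85 | Power at 0.95 |
|---|---|---|---|---|
| US | 128/140 | 0.855 / 0.846 | 0.01705 | 0.97629 |
| Pooled | 170/188 | 0.853 / 0.847 | 0.01939 | 0.99702 |

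Both sets exceed 102, hold 2.5% and have more than the planned power.

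**3. The two sets together.** Pooled successes are US successes plus an independent Binomial(48, p) count, so the joint probabilities are exact.
- At 0.85, P(both pass) = 0.00902. P(either passes) = 0.01705 + 0.01939 − 0.00902 = 0.02742, which is 0.24 percentage points above 2.5%.
- At 0.95, P(both pass) = 0.97589. US fails and pooled passes: 0.99702 − 0.97589 = 0.02113. US passes and pooled fails: 0.97629 − 0.97589 = 0.00040. Disagreement in total: 0.02153.
- Below the design value (assumed P30), disagreement is 6.4% at 0.94, 12.8% at 0.93 and 20.2% at 0.90.

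**4. Sensitivity to realised sizes.** Over an assumed grid of US 140–150 and China 48–55 (11 × 8 = 88 pairs), the either-set error runs from 2.13% to 3.54%, with median 2.78%. It exceeds 2.5% in 70 pairs and does not in the other 18. Over the same grid the US-only error is 1.34% to 2.40% and the pooled error 1.47% to 2.39%, so each set alone always holds its level.

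**5. What the text permits.** The either-set figures need a rule that either result is enough. Section 9.5 states one rule for the study, and Section 9.2 gives it one set. Section 9.9 sets no second criterion; it describes what may go into a submission. It says the completed non-US data will be included if available, so timing decides, not the US result. No visible passage schedules a US analysis before China finishes. The tGFR on the monitor is also not a P30 result, because the comparator comes from the two-compartment plasma fit in Section 9.4.

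**6. What a stricter rule would cost.** If the pooled set were tested only after US success, the chance of a pooled success at 0.95 would fall from 99.7% to 97.6%, because it becomes P(both pass). Making the US set alone decisive gives the same 97.6%. Either would replace the pooled reading of Sections 9.2 and 9.5 with one that depends on the US subset.

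**The case for a change.** The best case for a change is that it costs only a sentence and no subjects. Including the Chinese data does not say whether they are pooled or supportive, and conditional availability leaves the content to timing. The heading of Section 9.9 suggests staged analyses, so a US result could be known early. Borderline cases are easy to construct: 127/140 fails, but with 43/48 from China 170/188 passes; 128/140 passes, but with 41/48 from China 169/188 fails. Given a US failure at 0.95, the pooled set passes 89% of the time (0.02113 / 0.02371).

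The regions might also differ, since skin-type targets apply only in the US. With assumed P30 of 0.95 in the US and 0.80 in China, the US set passes and the pooled set fails in 27.7% of trials. With 0.90 and 0.95, the pooled set passes and the US set fails in 36.9%.

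The arithmetic is right, and the missing statement about the role of the Chinese data is real. Its weight is limited. The 89% conditions on an event of probability 2.4%, and the second borderline pattern occurs in 0.04% of trials at the design value. The large disagreement rates need a P30 well below the plan's 0.95, or regional differences that no figure in the documents supports. Disagreement between two sets is also not an error in itself: under the rule as written the pooled result decides study success, and the US result is one of its parts.

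**Conclusion.** No change follows. Read as written, the protocol has one primary set without regional limit and one success rule. Section 9.9 adds a statement about regulatory use, not a second route to success. What is missing is a detail: the label given to the US-only and Chinese results within the US application. Analysts can fill it sensibly by taking the pooled mITM result as the study's answer and showing the US result beside it. The alternatives that make the US set decisive are a trade-off, not a correction.

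The size is small. Error is 1.70% (US) or 1.94% (pooled) against 2.5%, and the verdicts differ in 2.2% of trials at the design value. An excess of 0.24 points arises at 140 + 48 only under a rule the plan does not state.

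This rests on the exact interval, equal P30 across regions and sizes near the plan. The Wilson interval gives the same pass marks. A Wald interval would not hold 2.5% in either set (5.65% US, 3.30% pooled), but that concerns the interval, not the dataset. The content of Appendix I and any separate SAP were not visible and may already settle the point.
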